The safety of patients will be monitored by collection of treatment-emergent AEs, SAEs, physical exams, vital signs, Holter monitoring and ECGs, PFTs, optical coherence tomography (OCT), blood chemistry and hematology panels, coagulation panels, and urinalysis at baseline and at various time points during the study. White blood cell (WBC) counts and lymphocyte counts will be monitored centrally (and will not be provided to the site) to prevent potential unblinding of the Investigator.

Patients who discontinue from treatment due to lack of response, AEs, or other reasons, even if alternative treatment is given, will be followed for 90 days for collection of safety data and for the assessment of their disease status.

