12.1. Adverse Events

The AE definitions and reporting procedures provided in this protocol comply with current CFR 21 Part 312.32. An AE is any untoward medical occurrence that does not necessarily have a causal relationship with the investigational medicinal product. An AE can therefore be any unfavorable or unintended sign, including an abnormal laboratory finding, symptom or disease temporally associated with the use of an investigational medicinal product whether or not considered related to the investigational medicinal product.

UC disease relapse and related symptoms will be monitored as study endpoints, but will not be recorded as AEs.

AEs will be monitored throughout the entire study including the 90-day Safety Follow-up Visit. Investigators will ask the patient at each visit if they have experienced any untoward occurrence since the last study visit. All AEs will be recorded on the eCRFs provided: a description of the event, severity, time of occurrence, duration, any action (e.g., treatment and follow-up tests), and the outcome should be provided along with the Investigator's assessment of the relationship to the investigational drug.

AEs will be recorded from the time written informed consent is signed until 90 days following the last dose of treatment with the investigational drug.

If known, the event diagnosis should be recorded, in preference to the listing of individual signs or symptoms. AEs must be graded as being mild, moderate, or severe and their approximate duration given. Definitions of severity are as follows:

Mild: an AE usually transient in nature and generally not interfering with normal activities;

Moderate: an AE that is sufficiently discomforting to interfere with normal activities;

Severe: an AE that is incapacitating and prevents normal activities.

Even if the Investigator feels there is no relationship to the investigational drug, all AEs MUST be recorded in the eCRF. The Investigator is requested to assess the relationship of any AEs to treatment using the following definitions:

Unrelated: those AEs which are clearly and incontrovertibly due to extraneous causes (concurrent drugs, environment etc.) and do not meet the criteria for drug relationship listed under Unlikely, Possible, Probable or Related.

Unlikely: an AE may be considered unlikely if it includes at least the first two features:

- It does not follow a reasonable temporal sequence from administration of the drug.

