12.3. Reporting of Serious Adverse Events

Investigator reporting requirements for SAEs will be managed on behalf of the Sponsor by PPD. Full details of the procedures to be adopted will be documented in a safety management plan approved by responsible parties, in brief:

Any SAE which occurs to any patient from the time written informed consent is signed through the last visit must be reported by the Investigator. All SAEs that occur within 90 days of the last dose of treatment with the investigational drug, whether or not considered related to the investigational product, must also be reported. Any SAE that is ongoing when the patient completes the study or discontinues from the study will be followed by the Investigator until the event has resolved, stabilized, or returned to baseline status or the patient is lost to follow-up.

Any AE considered serious by the Investigator or Sub-Investigator or that meets serious criteria should be reported to PPD Pharmacovigilance (PVG) using the remote data capture (RDC) system. Data entry must be completed within 24 hours from the time the study site personnel first learned of the event.

In the event that RDC entry is not possible (e.g., system failure or access problems), the study site should complete the paper SAE report form and fax the form to PPD PVG within 24 hours of awareness of the event. The RDC system should be updated as soon as it is available.

Contact information for the PPD Pharmacovigilance Center:

SAE [contact]

SAE Fax line: [name]

The initial report should be promptly followed by detailed, written reports, which will include copies of hospital case records, discharge summaries, autopsy reports and other documents when requested and applicable. For unrelated cases, a full detailed case description may negate the need for additional hospital case records, discharge summaries, etc.

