the MP will occur at Week 32. Patients who complete the MP will be given the option to participate in the OLP. Patients that enter the MP and experience disease relapse will have the option to enter the OLP.

Optional Open-Label Treatment Period (OLP)

Patients who complete the IP and are non-responders at Week 8 and those that complete the MP or experience disease relapse during the MP will have the option to enter the OLP. All patients in the OLP will receive daily study treatment with RPC1063 1.0 mg. There will be an 8 day dose titration regimen consisting of 4 days of treatment with 0.25 mg RPC1063, followed by 3 days treatment with RPC1063 0.5 mg, followed by RPC1063 1.0 mg. Patients who are non-responders 8 weeks after initiation of the OLP should discontinue from the study. The OLP will continue until the last patient who enters the OLP portion of the study has completed 20 weeks of treatment in the OLP.

[figure not shown]
Safety Monitoring/Follow-up

Potential adverse events (AEs) of interest that may be a consequence of sphingosine 1-phosphate 1 receptor 1 (S1P1R) modulation will be closely monitored during the study. These AEs include bradycardia and heart conduction abnormalities, pulmonary toxicity, macular edema, cutaneous malignancy, serious or opportunistic infection and hepatotoxicity. A Data Monitoring Committee (DMC) for the study will perform safety reviews periodically, approximately four times a year.

The safety of patients will be monitored by collection of treatment-emergent AEs, SAEs, physical exams, vital signs, Holter monitoring and ECGs, Pulmonary Function Tests (PFTs), optical coherence tomography (OCT), dermatologic exams, blood chemistry and hematology panels, coagulation panels, and urinalysis at baseline and at various time points during the study. White blood cell (WBC) counts and lymphocyte counts will be monitored centrally (and will not be provided to the site) to prevent potential unblinding of the Investigator.

Patients who discontinue from treatment due to lack of response, AEs, or other reasons, even if alternative treatment is given, will be followed for 30 days for collection of safety data, including lymphocyte recovery, and for the assessment of their disease status.

Figure 1: Study Schematic

5. **DEFINITIONS**

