5.3. Safety Definitions

AE or SAE Onset Date

AE and SAE onset or start dates are reported in the AE eCRFs.

AE or SAE End Date

AE and SAE end dates are reported in the AE eCRFs.

AEs and SAEs

AEs will be recorded from the time written informed consent is signed through the Follow-up visit (last dose + 30 days).

An AE or SAE will be regarded as treatment-emergent if it has a start date during or after the first study drug administration or if it worsened or if the relationship to study drug changed from unrelated to related after the first study drug administration. UC disease relapse and related symptoms will be monitored as study endpoints, but will not be recorded as AEs unless they meet the definition of an SAE.

All AEs or SAEs meeting these criteria with a start date up to and including 30 days following the last dose of treatment with the study drug will be considered treatment-emergent.

Treatment Related AEs

For summary purposes, all AEs classified by the Investigator on the AE eCRF as "possible", "probable" or "related" will be considered treatment related AEs. If the relationship to study drug is unknown or missing, the AE will be considered to be treatment related.

Duration of AEs

The duration of an AE will be calculated as:

Duration = (AE End Date - AE Onset Date) + 1

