7.3. Visit Windows

Post-OLP-Baseline visits (scheduled or unscheduled) during OLP will be mapped to an analysis visit based on the windowing algorithm below. If a visit cannot be mapped to any analysis visit, then the analysis visit will be set to missing and the data of interest will be excluded from summaries. If multiple visits containing the same data of interest can be mapped to the same analysis visit, the visit closest to the target day will be used in the analysis. In the event that two or more visits are equidistant to the target day, the later visit will be used in the analysis. If the two visits are on the same day, then the visit with the worst result will be used in the analysis.

Visit	Target Day	Analysis Visit Window for partial Mayo score	Analysis Visit Window for Complete Mayo Score, 9-point Mayo Score and Geboes Index
		(+/- 6 weeks)	(+/- 24 weeks)
Day 1OLP	1	N/A	N/A
Week 4OLP	36	(19-50)	N/A
Week 8OLP	64	(51 - 106)	N/A
Week 20OLP	148	(107 - 190)	N/A
Week 32OLP	232	(191 - 274)	N/A
Week 44OLP	316	(275 - 358)	N/A
Week 56OLP	400	(359 - 442)	(232 - 568)
Week 68OLP	484	(443 - 526)	N/A
Week 80OLP	568	(527 - 610)	N/A
Week 92OLP	652	(611 - 694)	N/A

Week 104OLP	736	(695 - 778)	(569 - 904)
Week 116OLP	820	(779 - 862)	N/A
Week 128OLP	904	(863 - 946)	N/A
Week 140OLP	988	(947 - 1030)	N/A
Week 152OLP	1072	(1031 - 1114)	(905 - 1240)
Week 164OLP	1156	(1115 - 1198)	N/A
Week 176OLP	1240	(1199 - 1282)	N/A
Week 188OLP	1324	(1283 - 1366)	N/A
Week 200OLP	1408	(1367 - 1450)	(1241 - 1576)
Week 212OLP	1492	(1451 - 1534)	N/A
Week 224OLP	1576	(1535 - 1618)	N/A
Week 236OLP	1660	(1619 - 1702)	N/A
Week 248OLP	1744	(1703 - 1786)	(1577 - 1912)
Week 260OLP	1828	(1787 - 1870)	N/A
Week 272OLP	1912	(1871 - 1954)	N/A
Week 284OLP	1996	(1955 - 2038)	N/A
Week 296OLP	2080	(2039 - 2122)	(1913 - 2248)
Week 308OLP	2164	(2123 - 2206)	N/A
Week 320OLP	2248	(2207 - 2290)	N/A

8. Safety Analyses

AEs will be recorded from the time written informed consent is signed through the 90-day safety Follow-up visit to ensure adequate collection of adverse events that could be associated with investigational drug.

Treatment-emergent adverse events include adverse events that started between the date of first dose of OLP and 90-day safety Follow-up visit after the date of last dose.

9. Guideline on Missing Date Imputation

The following missing data imputation rules will be applied to the OLP analyses.

Medication Dates:

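### The core SAP stops adverse-event recording and treatment-emergence 30 days after last dose against the protocol's 90-day recording, so day 31–90 events in patients who never enter the OLP miss the placebo-controlled treatment-emergent tables

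*SAP*

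**What the plan says.** **Core SAP.** Section 5.3 has AEs recorded from consent "through the Follow-up visit (last dose + 30 days". It treats qualifying events as treatment-emergent when they occur "with a start date up to and including 30 days following the last dose of treatment with the study drug". The preceding condition in that section sets only a lower limit (first dose or worsening), so this sentence supplies the upper one. Section 4 says that patients who discontinue "will be followed for 30 days for collection of safety data, including lymphocyte recovery".

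**Protocol.** Section 12.1 records AEs "until 90 days following the last dose of treatment with the investigational drug". Section 12.3 brings in "All SAEs that occur within 90 days of the last dose of treatment with the investigational drug", whether or not related. Section 9.1 says that patients who discontinue "will be followed for 90 days for collection of safety data and for the assessment of their disease status". Table 1, which covers the Induction Period (IP) and Maintenance Period (MP), schedules a visit at last dose + 90 ± 10 days. Its footnote r requires AEs to be recorded there even when the visit is replaced by a telephone call. Section 13.10 calls for treatment-emergent summaries but gives no post-dose cut-off.

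**OLP addendum.** Section 8 states: "Treatment-emergent adverse events include adverse events that started between the date of first dose of OLP and 90-day safety Follow-up visit". The window opens at the first OLP dose, so it does not alter the rule for the randomized periods.

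**SAP Section 8 (deviations from protocol).** It lists histologic remission and plasma biomarkers only. The 30-day limit is not mentioned.

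**The concern.** The IP and MP are the only placebo-controlled safety data in the trial. The core SAP departs from the protocol on how long AEs are recorded and patients followed, and it builds the treatment-emergent definition on the shorter period. An event 45 days after last dose would be treatment-emergent in the OLP tables and not in the randomized comparison.

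The patients exposed to the shorter rule are not a random subset. Under protocol Sections 9.1 and 10.4 the OLP is open to Week 8 non-responders who complete the IP, to MP completers and to patients who relapse in the MP. A patient who stops early because of an AE generally meets none of these conditions. The protocol also expects effects to outlast dosing: Section 10.5 continues lymphocyte testing after permanent discontinuation until recovery. Infections are among the AEs of special interest in SAP Section 6.20.1.

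**Working it through.** The plan gives no figure of its own to reproduce here. The check sets the day limits side by side and then does simple arithmetic.

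| Item | Core SAP | Protocol (IP/MP) | OLP addendum |
|---|---|---|---|
| AE recording ends | last dose + 30 days (5.3) | last dose + 90 days (12.1, 12.3) | 90-day visit (8) |
| Follow-up after discontinuation | 30 days (4) | 90 days (9.1) | not restated |
| Treatment-emergence ends | last dose + 30 days (5.3) | not specified (13.10) | 90-day visit, from first OLP dose (8) |

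**1. Share of the post-treatment window left out.** (90 − 30)/90 = 60/90 = 66.7%. With the 30-day rule fixed and the 90-day visit anywhere in its ±10-day window, the share runs from (80 − 30)/80 = 62.5% to (100 − 30)/100 = 70.0%.

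**2. Total counted time per affected patient.** This assumes that the last dose falls on the nominal visit day in Table 1.

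| Last dose | Counted to +30 | Counted to +90 | Shortfall |
|---|---|---|---|
| Day 36 (Week 4) | 66 | 126 | 60/126 = 48% |
| Day 64 (Week 8) | 94 | 154 | 60/154 = 39% |
| Day 232 (Week 32) | 262 | 322 | 60/322 = 19% |

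**3. Who is affected.** Protocol Section 10.4 requires OLP entrants to start within 2 weeks of the qualifying visit, and SAP Section 5.4 includes RPC1063 1.0 mg in study drug. Their last dose therefore falls in the OLP, and neither cut-off is reached before dosing resumes. Only patients who stop without entering the OLP lose the 60 days.

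**4. Size across the trial.** The share of the 180 randomized patients who never enter the OLP is not in the documents, so the values below are assumptions. Uncounted patient-days = 180 × share × 60:

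- 5%: 540
- 10%: 1,080
- 25%: 2,700
- 50%: 5,400

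**5. Which outputs are affected.** In SAP Section 6.20.1 the main AE incidence tables by system organ class and preferred term are defined on treatment-emergent events. The overview row for any SAE and the AE, SAE and death listings are not worded that way, so later events could appear there. However, Section 5.3 also ends recording at 30 days, so these outputs cannot be relied on to carry them.

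**The case against.** **A recording window is not a treatment-emergent window.** This stands. The protocol sets no treatment-emergent cut-off, so a 30-day limit does not by itself contradict its analysis section. There is also a case for 30 days. The protocol's own contents list separates concomitant-medication rules before and after the 30-day visit, and Section 9.1 continues follow-up even when alternative treatment is given. Events after day 30 may therefore reflect other therapy. None of this explains the SAP's statements on recording and follow-up, which do conflict with the protocol.

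**The day 31–90 data may not exist for every patient.** This also stands. The core SAP appears to follow an earlier protocol version: it ends the OLP after 20 weeks of treatment for the last entrant (against up to 6 years in the protocol) and analyses Day 5 cardiac monitoring that protocol Table 4 does not show. A reader might infer that the 90-day data are already in hand and that only a programming parameter must change. The documents do not show that 90-day collection was in force when each IP or MP patient stopped.

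**The addendum's reasoning.** A reader might take the addendum to justify its 90-day treatment-emergent window by the need for adequate collection. That reason is attached to its sentence on recording; the treatment-emergent sentence gives none.

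**Practical weight.** SAP Section 6.20 plans no hypothesis tests on safety, and no formal comparison of core with OLP incidence is specified. This limits the consequence but does not remove the mismatch in the descriptive tables.

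**Conclusion.** The concern holds in a limited form. The core SAP is out of step with the protocol on AE recording and follow-up. As written, it leaves 60 of 90 post-treatment days out of the placebo-controlled treatment-emergent tables for patients who stop in the IP or MP and do not enter the OLP. The core and OLP tables then rest on different definitions, and the SAP does not declare the difference.

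The 67% is a share of calendar time after last dose for each affected patient. A reader might infer that two thirds of post-treatment events, or of the whole randomized population's safety follow-up, are lost. The documents do not support that: OLP entrants are unaffected, the number of other patients is not given, and no event rates are available. Nor do the documents show that later events vanish from every output.

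The conclusion rests on reading Section 5.3 as an upper limit and on the current protocol text governing IP/MP follow-up. Efficacy analyses are not touched.

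**What to change.** 1. Change the recording statement in SAP Section 5.3 and the follow-up statement in Section 4 to 90 days after last dose, to match the protocol.
2. Summarize AEs and SAEs to 90 days after last dose by randomized-period treatment group, censored at the first OLP or extension-study dose. Do this in one of two ways: make 90 days the treatment-emergent window, as in the addendum, and keep the 30-day table alongside; or retain 30 days with a stated justification and add a separate by-arm table for days 31–90.
3. Report how many IP and MP patients had 90-day collection in force.
4. SAP Section 6.10 unblinds the IP and MP groups at the primary analysis. If the change comes after that, label it as made after unblinding.

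The cost is SAP wording and one extra set of tables. The downside is that events after day 30 may reflect alternative therapy, which a footnote to the later-window table should say.

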5.4. Other Definitions

Age

Age (in years) will be calculated from the date of birth to the date of informed consent. Age will be reported as an integer.

Study Drug

Study drug refers to RPC1063 0.5 mg, RPC1063 1.0 mg, or Placebo oral capsules as well as the titration doses.

6. STATISTICAL METHODS

This section presents the statistical approaches that are anticipated for the analysis of study data. These approaches may at times require modifications due to unanticipated features of the data. Any modifications that are not in the final SAP are considered to be post-hoc and will be detailed in the CSR.

6.1. General Analysis Approach

Unless otherwise noted, all summaries of data by treatment group during the IP/MP and the OLP will include the following three groups:

- 1) Placebo
- 2) RPC1063 0.5 mg
- 3) RPC1063 1.0 mg

The following conventions will be used for all data presentations and analyses unless otherwise specified.

- Appropriate descriptive statistics will be computed and displayed (by time point and other key variables as appropriate) for both continuous and categorical variables. For continuous variables, descriptive statistics will include n (the number of patients with non-missing data), mean, standard deviation (SD), median, and minimum and maximum values. For categorical data, the number and percentage of patients within each category will be presented. The denominator for percentages will be based on the number of patients with non-missing data appropriate for summary purposes. Unless otherwise noted, all percentages will be presented to one decimal place.
- Individual data listings of all data represented on the eCRF and from the clinical laboratory will be presented. Sort order for data listings will be treatment, site-patient number, visit, and assessment period where appropriate.
- Version 9.1 (or higher) of the SAS® statistical software package will be used to provide all tables, figures, data listings, and analyses.

• There are approximately 70 study sites in this study. Due to the large number of study sites and the small numbers of patients per site, the analysis of efficacy endpoints will not include adjustments for study site.

Further analysis and reporting conventions are described in Section 7.

6.2. Coding Dictionaries

Adverse events will be coded using version 15.0 or later of the Medical Dictionary for Regulatory Activities (MedDRA). Prior and concomitant medications will be coded according to the World Health Organization Drug Dictionary, Enhanced, September 1, 2012 or later.

6.3. Data Management

An eCRF will be used for the current study, and a data management plan will be prepared by the contract research organization (CRO), PPD.

6.4. Missing values

The Mayo score used for clinical endpoints in the study will utilize the Mayo endoscopy score derived from the central reader. In the case that a central endoscopic result is missing the endoscopic subscore read by the Investigator will be utilized.

For calculation of the Mayo score for the efficacy endpoints, at least 2 of the 4 subscores must be available to calculate the total Mayo score. A missing subscore(s) will be carried forward from the most recent previous visit for which the subscore is available. The endoscopy subscore is not considered missing if the Investigator endoscopic subscore is available. If more than 2 subscores are missing, then the Mayo score will be considered missing.

For calculation of the partial Mayo score for the efficacy endpoints, at least 2 of the 3 subscores must be available to calculate the partial Mayo score. The missing subscore will be carried forward from the previous visit. If more than 1 subscore is missing, then the partial Mayo score will be considered missing.

For the primary analysis, as well as for the analyses of all key secondary efficacy endpoints that are defined as proportions, patients who have missing Mayo or partial Mayo scores at the specified time point will be classified as nonresponders.

One of the key secondary efficacy endpoints (change in Mayo score) is a quantitative endpoint. For the key secondary analysis of this variable, missing values will be replaced by the last observation carried forward (LOCF). If no post-Baseline observation is available to carry forward, then the average score for the observed values within the same treatment group will be used, rounded to the nearest integer.

